#### 11.4.2 RASH – SMQ19.1

##### SMQ 19.1: “Severe cutaneous adverse reaction” : all narrow and selected broad terms

SCOPE	Preferred Term
NARROW	CUTANEOUS VASCULITIS
NARROW	DERMATITIS BULLOUS
NARROW	DERMATITIS EXFOLIATIVE
NARROW	DERMATITIS EXFOLIATIVE GENERALISED
NARROW	ERYTHEMA MULTIFORME
NARROW	OCULOMUCOCUTANEOUS SYNDROME
NARROW	SKIN NECROSIS
NARROW	STEVENS-JOHNSON SYNDROME
NARROW	TOXIC EPIDERMAL NECROLYSIS
NARROW	ACUTE GENERALISED EXANTHEMATOUS PUSTULOSIS
NARROW	TOXIC SKIN ERUPTION
NARROW	EPIDERMAL NECROSIS
NARROW	EXFOLIATIVE RASH
NARROW	DRUG REACTION WITH EOSINOPHILIA AND SYSTEMIC SYMPTOMS
BROAD	BLISTER
BROAD	BULLOUS IMPETIGO
BROAD	DRUG ERUPTION
BROAD	EPIDERMOLYSIS BULLOSA
BROAD	MUCOCUTANEOUS ULCERATION
BROAD	NIKOLSKY'S SIGN
BROAD	PEMPHIGOID
BROAD	PEMPHIGUS
BROAD	SKIN EROSION
BROAD	SKIN EXFOLIATION
BROAD	EPIDERMOLYSIS
BROAD	ACQUIRED EPIDERMOLYSIS BULLOSA

## 11.4.3 CARDIAC EVENTS - SMQ19.1

			Narrow/Broad	PT Term
Cardiac arrhythmias (SMQ)				
Arrhythmia related investigations, signs and symptoms (SMQ)				
			Narrow	Chronotropic incompetence
			Narrow	Electrocardiogram repolarisation abnormality
			Narrow	Electrocardiogram RR interval prolonged
			Narrow	Electrocardiogram U-wave abnormality
			Narrow	Sudden cardiac death
			Broad	Bezold-Jarisch reflex
			Broad	Bradycardia
			Broad	Cardiac arrest
			Broad	Cardiac death
			Broad	Cardiac telemetry abnormal
			Broad	Cardio-respiratory arrest
			Broad	Central bradycardia
			Broad	Electrocardiogram abnormal
			Broad	Electrocardiogram ambulatory abnormal
			Broad	Electrocardiogram change
			Broad	Heart rate abnormal
			Broad	Heart rate decreased
			Broad	Heart rate increased
			Broad	Loss of consciousness
			Broad	Palpitations
			Broad	Rebound tachycardia
			Broad	Sudden death
			Broad	Syncope
			Broad	Tachycardia
			Broad	Tachycardia paroxysmal
Cardiac arrhythmia terms (incl bradyarrhythmias and tachyarrhythmias) (SMQ)				
Bradyarrhythmias (incl conduction defects and disorders of sinus node function) (SMQ)				
Bradyarrhythmia terms, nonspecific (SMQ)				
			Narrow	Bradyarrhythmia
			Narrow	Ventricular asystole
Conduction defects (SMQ)				
			Narrow	Accessory cardiac pathway
			Narrow	Adams-Stokes syndrome
			Narrow	Agonal rhythm

			Narrow	Atrial conduction time prolongation
			Narrow	Atrioventricular block
			Narrow	Atrioventricular block complete
			Narrow	Atrioventricular block first degree
			Narrow	Atrioventricular block second degree
			Narrow	Atrioventricular conduction time shortened
			Narrow	Atrioventricular dissociation
			Narrow	Bifascicular block
			Narrow	Brugada syndrome
			Narrow	Bundle branch block
			Narrow	Bundle branch block bilateral
			Narrow	Bundle branch block left
			Narrow	Bundle branch block right
			Narrow	Conduction disorder
			Narrow	Defect conduction intraventricular
			Narrow	Electrocardiogram delta waves abnormal
			Narrow	Electrocardiogram PQ interval prolonged
			Narrow	Electrocardiogram PQ interval shortened
			Narrow	Electrocardiogram PR prolongation
			Narrow	Electrocardiogram PR shortened
			Narrow	Electrocardiogram QRS complex prolonged
			Narrow	Electrocardiogram QT prolonged
			Narrow	Electrocardiogram repolarisation abnormality
			Narrow	Lenegre's disease
			Narrow	Long QT syndrome
			Narrow	Paroxysmal atrioventricular block
			Narrow	Sinoatrial block
			Narrow	Trifascicular block
			Narrow	Ventricular dyssynchrony
			Narrow	Wolff-Parkinson-White syndrome
			Disorders of sinus node function (SMQ)	
			Narrow	Nodal arrhythmia
			Narrow	Nodal rhythm
			Narrow	Sinus arrest
			Narrow	Sinus arrhythmia
			Narrow	Sinus bradycardia
			Narrow	Sinus node dysfunction
			Narrow	Wandering pacemaker
			Cardiac arrhythmia terms, nonspecific (SMQ)	
			Narrow	Arrhythmia

			Narrow	Heart alternation
			Narrow	Heart rate irregular
			Narrow	Pacemaker generated arrhythmia
			Narrow	Pacemaker syndrome
			Narrow	Paroxysmal arrhythmia
			Narrow	Pulseless electrical activity
			Narrow	Reperfusion arrhythmia
			Narrow	Withdrawal arrhythmia
			Tachyarrhythmias (incl supraventricular and ventricular tachyarrhythmias) (SMQ)	
			Supraventricular tachyarrhythmias (SMQ)	
			Narrow	Arrhythmia supraventricular
			Narrow	Atrial fibrillation
			Narrow	Atrial flutter
			Narrow	Atrial parasystole
			Narrow	Atrial tachycardia
			Narrow	Junctional ectopic tachycardia
			Narrow	Sinus tachycardia
			Narrow	Supraventricular extrasystoles
			Narrow	Supraventricular tachyarrhythmia
			Narrow	Supraventricular tachycardia
			Broad	ECG P wave inverted
			Broad	Electrocardiogram P wave abnormal
			Broad	Retrograde p-waves
			Tachyarrhythmia terms, nonspecific (SMQ)	
			Narrow	Anomalous atrioventricular excitation
			Narrow	Cardiac fibrillation
			Narrow	Cardiac flutter
			Narrow	Extrasystoles
			Narrow	Tachyarrhythmia
			Ventricular tachyarrhythmias (SMQ)	
			Narrow	Accelerated idioventricular rhythm
			Narrow	Cardiac fibrillation
			Narrow	Parasystole
			Narrow	Rhythm idioventricular
			Narrow	Torsade de pointes
			Narrow	Ventricular arrhythmia
			Narrow	Ventricular extrasystoles
			Narrow	Ventricular fibrillation
			Narrow	Ventricular flutter

				Narrow	Ventricular parasystole
				Narrow	Ventricular pre-excitation
				Narrow	Ventricular tachyarrhythmia
				Narrow	Ventricular tachycardia
Cardiac failure (SMQ)					
				Narrow	Acute left ventricular failure
				Narrow	Acute pulmonary oedema
				Narrow	Acute right ventricular failure
				Narrow	Cardiac asthma
				Narrow	Cardiac failure
				Narrow	Cardiac failure acute
				Narrow	Cardiac failure chronic
				Narrow	Cardiac failure congestive
				Narrow	Cardiac failure high output
				Narrow	Cardiogenic shock
				Narrow	Cardiopulmonary failure
				Narrow	Cardiorenal syndrome
				Narrow	Chronic left ventricular failure
				Narrow	Chronic right ventricular failure
				Narrow	Cor pulmonale
				Narrow	Cor pulmonale acute
				Narrow	Cor pulmonale chronic
				Narrow	Ejection fraction decreased
				Narrow	Hepatic congestion
				Narrow	Hepatojugular reflux
				Narrow	Left ventricular failure
				Narrow	Low cardiac output syndrome
				Narrow	Neonatal cardiac failure
				Narrow	Obstructive shock
				Narrow	Pulmonary oedema
				Narrow	Pulmonary oedema neonatal
				Narrow	Radiation associated cardiac failure
				Narrow	Right ventricular ejection fraction decreased
				Narrow	Right ventricular failure
				Narrow	Ventricular failure
				Broad	Artificial heart implant
				Broad	Atrial natriuretic peptide abnormal
				Broad	Atrial natriuretic peptide increased
				Broad	Bendopnoea
				Broad	Brain natriuretic peptide abnormal

				Broad	Brain natriuretic peptide increased
				Broad	Cardiac cirrhosis
				Broad	Cardiac contractility modulation therapy
				Broad	Cardiac index decreased
				Broad	Cardiac output decreased
				Broad	Cardiac resynchronisation therapy
				Broad	Cardiac ventriculogram abnormal
				Broad	Cardiac ventriculogram left abnormal
				Broad	Cardiac ventriculogram right abnormal
				Broad	Cardiomegaly
				Broad	Cardio-respiratory distress
				Broad	Cardiothoracic ratio increased
				Broad	Central venous pressure increased
				Broad	Diastolic dysfunction
				Broad	Dilatation ventricular
				Broad	Dyspnoea paroxysmal nocturnal
				Broad	Heart transplant
				Broad	Hepatic vein dilatation
				Broad	Jugular vein distension
				Broad	Left ventricular dilatation
				Broad	Left ventricular dysfunction
				Broad	Left ventricular enlargement
				Broad	Lower respiratory tract congestion
				Broad	Myocardial depression
				Broad	Nocturnal dyspnoea
				Broad	N-terminal prohormone brain natriuretic peptide abnormal
				Broad	N-terminal prohormone brain natriuretic peptide increased
				Broad	Oedema
				Broad	Oedema due to cardiac disease
				Broad	Oedema neonatal
				Broad	Oedema peripheral
				Broad	Orthopnoea
				Broad	Peripheral oedema neonatal
				Broad	Peripheral swelling
				Broad	Post cardiac arrest syndrome
				Broad	Prohormone brain natriuretic peptide abnormal
				Broad	Prohormone brain natriuretic peptide increased
				Broad	Pulmonary congestion

				Broad	Right ventricular dilatation
				Broad	Right ventricular dysfunction
				Broad	Right ventricular enlargement
				Broad	Scan myocardial perfusion abnormal
				Broad	Stroke volume decreased
				Broad	Surgical ventricular restoration
				Broad	Systolic dysfunction
				Broad	Venous pressure increased
				Broad	Venous pressure jugular abnormal
				Broad	Venous pressure jugular increased
				Broad	Ventricular assist device insertion
				Broad	Ventricular dysfunction
				Broad	Ventricular dyssynchrony
Cardiomyopathy (SMQ)					
				Narrow	Atrial septal defect acquired
				Narrow	Biopsy heart abnormal
				Narrow	Cardiac amyloidosis
				Narrow	Cardiac hypertrophy
				Narrow	Cardiac sarcoidosis
				Narrow	Cardiac septal hypertrophy
				Narrow	Cardiac siderosis
				Narrow	Cardiomyopathy
				Narrow	Cardiomyopathy acute
				Narrow	Cardiomyopathy alcoholic
				Narrow	Cardiomyopathy neonatal
				Narrow	Cardiotoxicity
				Narrow	Congestive cardiomyopathy
				Narrow	Cytotoxic cardiomyopathy
				Narrow	Diabetic cardiomyopathy
				Narrow	Ejection fraction abnormal
				Narrow	Ejection fraction decreased
				Narrow	Eosinophilic myocarditis
				Narrow	HIV cardiomyopathy
				Narrow	Hypertensive cardiomyopathy
				Narrow	Hypertrophic cardiomyopathy
				Narrow	Ischaemic cardiomyopathy
				Narrow	Metabolic cardiomyopathy
				Narrow	Myocardial calcification
				Narrow	Myocardial fibrosis
				Narrow	Myocardial haemorrhage

				Narrow	Non-obstructive cardiomyopathy
				Narrow	Peripartum cardiomyopathy
				Narrow	Pulmonary arterial wedge pressure increased
				Narrow	Restrictive cardiomyopathy
				Narrow	Right ventricular ejection fraction decreased
				Narrow	Stress cardiomyopathy
				Narrow	Tachycardia induced cardiomyopathy
				Narrow	Thyrotoxic cardiomyopathy
				Narrow	Ventricular septal defect acquired
				Narrow	Viral cardiomyopathy
				Broad	Abnormal precordial movement
				Broad	Acquired cardiac septal defect
				Broad	Acute left ventricular failure
				Broad	Alcohol septal ablation
				Broad	Allergic myocarditis
				Broad	Arrhythmia
				Broad	Arrhythmia supraventricular
				Broad	Artificial heart implant
				Broad	Ascites
				Broad	Atrial hypertrophy
				Broad	Atrial pressure increased
				Broad	Autoimmune myocarditis
				Broad	Bendopnoea
				Broad	Blood pressure diastolic abnormal
				Broad	Blood pressure diastolic decreased
				Broad	Blood pressure diastolic increased
				Broad	Blood pressure fluctuation
				Broad	Blood pressure inadequately controlled
				Broad	Blood pressure systolic abnormal
				Broad	Blood pressure systolic decreased
				Broad	Blood pressure systolic increased
				Broad	Cardiac aneurysm
				Broad	Cardiac arrest
				Broad	Cardiac contractility modulation therapy
				Broad	Cardiac electrophysiologic study abnormal
				Broad	Cardiac failure
				Broad	Cardiac failure acute
				Broad	Cardiac failure chronic
				Broad	Cardiac failure congestive
				Broad	Cardiac function test abnormal

				Broad	Cardiac imaging procedure abnormal
				Broad	Cardiac index abnormal
				Broad	Cardiac index decreased
				Broad	Cardiac index increased
				Broad	Cardiac monitoring abnormal
				Broad	Cardiac operation
				Broad	Cardiac output decreased
				Broad	Cardiac pseudoaneurysm
				Broad	Cardiac resynchronisation therapy
				Broad	Cardiac ventricular scarring
				Broad	Cardiac ventriculogram abnormal
				Broad	Cardiac ventriculogram left abnormal
				Broad	Cardiac ventriculogram right abnormal
				Broad	Cardiomegaly
				Broad	Cardiothoracic ratio increased
				Broad	Cardiovascular disorder
				Broad	Cardiovascular function test abnormal
				Broad	Chest pain
				Broad	Chest X-ray abnormal
				Broad	Computerised tomogram thorax abnormal
				Broad	Coxsackie carditis
				Broad	Coxsackie myocarditis
				Broad	Cytomegalovirus myocarditis
				Broad	Decreased ventricular preload
				Broad	Diastolic dysfunction
				Broad	Dilatation atrial
				Broad	Dilatation ventricular
				Broad	Directional Doppler flow tests abnormal
				Broad	Dyspnoea
				Broad	ECG signs of ventricular hypertrophy
				Broad	Echocardiogram abnormal
				Broad	Electrocardiogram abnormal
				Broad	Electrocardiogram change
				Broad	Endocardial fibroelastosis
				Broad	External counterpulsation
				Broad	Gonococcal heart disease
				Broad	Heart and lung transplant
				Broad	Heart transplant
				Broad	Hepatomegaly
				Broad	Hyperdynamic left ventricle

				Broad	Increased ventricular preload
				Broad	Irregular breathing
				Broad	Labile blood pressure
				Broad	Left atrial dilatation
				Broad	Left atrial enlargement
				Broad	Left ventricular dilatation
				Broad	Left ventricular end-diastolic pressure decreased
				Broad	Left ventricular enlargement
				Broad	Left ventricular failure
				Broad	Left ventricular heave
				Broad	Lupus myocarditis
				Broad	Lyme carditis
				Broad	Malarial myocarditis
				Broad	Mental status changes
				Broad	Multiple gated acquisition scan abnormal
				Broad	Myocardial abscess
				Broad	Myocardial necrosis marker increased
				Broad	Myocarditis
				Broad	Myocarditis bacterial
				Broad	Myocarditis helminthic
				Broad	Myocarditis infectious
				Broad	Myocarditis meningococcal
				Broad	Myocarditis mycotic
				Broad	Myocarditis post infection
				Broad	Myocarditis septic
				Broad	Myocarditis syphilitic
				Broad	Myocarditis toxoplasmal
				Broad	Myoglobinaemia
				Broad	Myoglobinuria
				Broad	Nocturia
				Broad	Nuclear magnetic resonance imaging thoracic abnormal
				Broad	Oedema
				Broad	Orthostatic hypotension
				Broad	Palpitations
				Broad	Papillary muscle disorder
				Broad	Papillary muscle haemorrhage
				Broad	Radiation myocarditis
				Broad	Right atrial dilatation

				Broad	Right atrial enlargement
				Broad	Right atrial pressure increased
				Broad	Right ventricle outflow tract obstruction
				Broad	Right ventricular dilatation
				Broad	Right ventricular enlargement
				Broad	Right ventricular heave
				Broad	Right ventricular systolic pressure decreased
				Broad	Scan myocardial perfusion abnormal
				Broad	Sudden cardiac death
				Broad	Sudden death
				Broad	Surgical ventricular restoration
				Broad	Syncope
				Broad	Systolic anterior motion of mitral valve
				Broad	Systolic dysfunction
				Broad	Ultrasound Doppler abnormal
				Broad	Vascular resistance pulmonary increased
				Broad	Ventricular arrhythmia
				Broad	Ventricular assist device insertion
				Broad	Ventricular dysfunction
				Broad	Ventricular dyskinesia
				Broad	Ventricular dyssynchrony
				Broad	Ventricular hyperkinesia
				Broad	Ventricular hypertrophy
				Broad	Ventricular hypokinesia
				Broad	Ventricular remodelling
				Broad	Viral myocarditis
Ischaemic heart disease (SMQ)					
Myocardial infarction (SMQ)					
				Narrow	Acute coronary syndrome
				Narrow	Acute myocardial infarction
				Narrow	Angina unstable
				Narrow	Blood creatine phosphokinase MB abnormal
				Narrow	Blood creatine phosphokinase MB increased
				Narrow	Coronary artery embolism
				Narrow	Coronary artery occlusion
				Narrow	Coronary artery reocclusion
				Narrow	Coronary artery thrombosis
				Narrow	Coronary bypass thrombosis
				Narrow	Coronary vascular graft occlusion
				Narrow	Kounis syndrome

			Narrow	Myocardial infarction
			Narrow	Myocardial necrosis
			Narrow	Myocardial reperfusion injury
			Narrow	Myocardial stunning
			Narrow	Papillary muscle infarction
			Narrow	Post procedural myocardial infarction
			Narrow	Postinfarction angina
			Narrow	Silent myocardial infarction
			Narrow	Troponin I increased
			Narrow	Troponin increased
			Narrow	Troponin T increased
			Broad	Blood creatine phosphokinase abnormal
			Broad	Blood creatine phosphokinase increased
			Broad	Cardiac ventricular scarring
			Broad	ECG electrically inactive area
			Broad	ECG signs of myocardial infarction
			Broad	Electrocardiogram Q wave abnormal
			Broad	Electrocardiogram ST segment abnormal
			Broad	Electrocardiogram ST segment elevation
			Broad	Electrocardiogram ST-T segment elevation
			Broad	Infarction
			Broad	Myocardial necrosis marker increased
			Broad	Scan myocardial perfusion abnormal
			Broad	Vascular graft occlusion
			Broad	Vascular stent occlusion
			Broad	Vascular stent thrombosis
Shock (SMQ)				
Shock-associated circulatory or cardiac conditions (excl torsade de pointes) (SMQ)				
			Narrow	Acute left ventricular failure
			Narrow	Adams-Stokes syndrome
			Narrow	Atrial parasystole
			Narrow	Cardiac arrest
			Narrow	Cardiac arrest neonatal
			Narrow	Cardiac death
			Narrow	Cardiac fibrillation
			Narrow	Cardiac flutter
			Narrow	Cardiogenic shock
			Narrow	Cardio-respiratory arrest
			Narrow	Cardio-respiratory arrest neonatal

				Narrow	Cardiovascular insufficiency
				Narrow	Circulatory collapse
				Narrow	Obstructive shock
				Narrow	Pulse absent
				Narrow	Pulseless electrical activity
				Narrow	Shock
				Narrow	Shock symptom
				Narrow	Sudden cardiac death
				Narrow	Ventricular asystole
				Narrow	Ventricular fibrillation
				Narrow	Ventricular flutter
				Narrow	Ventricular parasystole
				Broad	Acute kidney injury
				Broad	Acute prerenal failure
				Broad	Acute respiratory failure
				Broad	Anuria
				Broad	Blood pressure immeasurable
				Broad	Cerebral hypoperfusion
				Broad	Grey syndrome neonatal
				Broad	Hepatic congestion
				Broad	Hepatojugular reflux
				Broad	Hepatorenal failure
				Broad	Hypoperfusion
				Broad	Jugular vein distension
				Broad	Myocardial depression
				Broad	Neonatal anuria
				Broad	Neonatal multi-organ failure
				Broad	Neonatal respiratory failure
				Broad	Organ failure
				Broad	Prerenal failure
				Broad	Propofol infusion syndrome
				Broad	Renal failure
				Broad	Renal failure neonatal
				Broad	Respiratory failure
Torsade de pointes/QT prolongation (SMQ)					
				Narrow	Electrocardiogram QT interval abnormal
				Narrow	Electrocardiogram QT prolonged
				Narrow	Long QT syndrome
				Narrow	Long QT syndrome congenital
				Narrow	Torsade de pointes

				Narrow	Ventricular tachycardia
				Broad	Cardiac arrest
				Broad	Cardiac death
				Broad	Cardiac fibrillation
				Broad	Cardio-respiratory arrest
				Broad	Electrocardiogram repolarisation abnormality
				Broad	Electrocardiogram U-wave abnormality
				Broad	Loss of consciousness
				Broad	Sudden cardiac death
				Broad	Sudden death
				Broad	Syncope
				Broad	Ventricular arrhythmia
				Broad	Ventricular fibrillation
				Broad	Ventricular flutter
				Broad	Ventricular tachyarrhythmia

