In the Phase 2a study C202, treatment-naïve subjects with HCV genotypes 2, 3, 4, 5, and 6 infection were treated with SMV 200 mg qd monotherapy for 7 days. Monotherapy with oral SMV 200 mg qd for 7 days showed potent antiviral activity against HCV GT2, 4, 5, and 6. For the primary endpoint at Day 8, the mean (\pm standard error [SE]) change in plasma HCV RNA (\log_{10} IU/mL) from baseline was the greatest for genotypes 6 (-4.35 ± 0.29) and 4 (-3.52 ± 0.43), followed by genotypes 2 (-2.73 ± 0.71) and 5 (-2.19 ± 0.39). No clear antiviral activity with SMV monotherapy was observed against HCV GT3. The efficacy in HCV GT4-infected subjects was confirmed in the Phase 3 study HPC3011.

SMV at a dose of 100 mg qd in combination with PegIFN/RBV has demonstrated good efficacy and a favorable safety/tolerability profile in Japanese HCV GT1 treatment-naïve and treatment-experienced subjects and the exposure at this dose was similar to the exposure of 150 mg qd in Caucasian subjects.

In HCV GT1b treatment-naïve subjects from China and South Korea, SMV 100 mg and 150 mg were found equally efficacious, with efficacy data in line with efficacy data previously obtained in mainly Caucasian treatment-naïve HCV GT1b-infected subjects dosed with SMV 150 mg qd.

Safety

The most common AEs reported in the Phase 3 trial of SMV with PegIFN and RBV (occurring with at least 3% higher frequency compared to placebo) during the first 12 weeks of treatment included: rash (including photosensitivity), pruritus, nausea, myalgia, and dyspnea. Most of the rash events were of mild or moderate severity (Grade 1 or Grade 2). Severe (Grade 3) rash occurred in 1% of SMV-treated subjects and there were no reports of life-threatening (Grade 4) rash. Discontinuation of SMV or placebo due to rash occurred in 1% of SMV-treated subjects, compared to less than 1% of placebo-treated subjects. The frequencies of rash and photosensitivity reactions were higher in subjects with higher SMV exposures. Most

photosensitivity reactions were of mild or moderate severity (Grade 1 or 2). Two SMV-treated subjects experienced photosensitivity reactions which resulted in hospitalization. No life-threatening photosensitivity reactions were reported.

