The incidence rates for each event of interest by WHO toxicity grades and relationship to study drugs will be summarized. Time to the first occurrence of the events of interest will be summarized and Kaplan-Meier curves will be plotted.

The incidence and comparable prevalence rate per 2-week time interval for AEs of special interest will be summarized and plotted by cohort.

Bar graphs of the worst toxicity grade of cardiac events over time by cohort will be plotted.

All adverse events for subjects who met the Study Stopping Rules (i.e. <1 log decline in HCV RNA after 4 weeks of treatment) will be listed.

All TEAEs reported in the CRF will be listed with the SOC, PT and investigator's verbatim. Additional listings will be provided for serious adverse events (SAEs), TEAEs with grade 3 or grade 4, TEAEs leading to any study drug discontinuation, TEAEs of special interest, and TEAEs with fatal outcome.

In case of rash, all information related to rash assessments will be listed.

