#### 11.4 Appendix 4: Events of special/clinical interest

##### 11.4.1 Search terms for Events of Special/Clinical Interest

	MedrDRA Term Level	Searching Terms
Events of special interest		
Cardiac Events	SMQ	Cardiac arrhythmias (SMQ) [Arrhythmia related investigations, signs and symptoms (SMQ); Cardiac arrhythmia terms (incl bradyarrhythmias and tachyarrhythmias) (SMQ)]; Cardiac failure (SMQ); Cardiomyopathy (SMQ); Ischaemic heart disease (SMQ)[ Myocardial infarction (SMQ)]; Shock (SMQ)[ Shock-associated circulatory or cardiac conditions (excl torsade de pointes) (SMQ)]; Torsade de pointes/QT prolongation (SMQ);  Please see Appendix 3
Increased Bilirubin	MedDRA PTs	Bilirubin conjugated abnormal Bilirubin conjugated increased Bilirubin excretion disorder Bilirubinuria Blood bilirubin abnormal Blood bilirubin increased Blood bilirubin unconjugated increased Hyperbilirubinaemia Icterus index increased Jaundice Jaundice cholestatic Jaundice extrahepatic obstructive Jaundice hepatocellular Ocular icterus Urine bilirubin increased Yellow skin
Events of clinical interest		
Rash (all type)	MedDRA HLT, PTs	Erythemas - HLT Papulosquamous conditions - HLT Rashes, eruptions and exanthems NEC - HLT PT: Photodermatosis

		Photosensitivity reaction Polymorphic light eruption Solar dermatitis Sunburn
	SMQ	SMQ-Severe cutaneous adverse reaction: All narrow terms and selected broad terms (refer APPENDIX 2B below)
Pruritus	MedDRA HLT	Pruritus NEC
Photosensitivity conditions	MedDRA PTs	Photodermatosis Photosensitivity reaction Polymorphic light eruption Solar dermatitis Sunburn

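### The grouped cardiac event of special interest pools narrow and broad search terms without a scope rule and leaves out angina pectoris and myocardial ischaemia, so its summaries are diluted

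*SAP*

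**What the plan says.** SAP 8.1 names cardiac events as a TEAE group of special interest and refers to Appendix 4 for the definition. Events of interest are reported as a summary table, by grade, by relationship to study drug, as time to first occurrence with Kaplan-Meier curves, and as incidence and prevalence per 2-week interval. Cardiac events also get their own figure: "Bar graphs of the worst toxicity grade of cardiac events over time by cohort will be plotted".

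SAP 11.4.1 sets the cardiac search at SMQ level, in part as "Cardiac failure (SMQ); Cardiomyopathy (SMQ); Ischaemic heart disease (SMQ)[ Myocardial infarction (SMQ", with no statement of narrow or broad scope. It points to Appendix 3 for the terms, but Appendix 3 is the list of tables. The terms are in 11.4.3, headed "CARDIAC EVENTS - SMQ19.1", where each is marked Narrow or Broad. Broad entries include "Hepatomegaly" (cardiomyopathy SMQ) and "Blood creatine phosphokinase increased" (myocardial infarction SMQ).

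For the severe cutaneous SMQ used under rash, the same appendix does fix the scope: "All narrow terms and selected broad terms" in 11.4.1, and "all narrow and selected broad terms" in the heading of the rash term list.

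**The concern.** Protocol 1.3 names the heart as a target organ of odalasvir toxicity, and safety is the primary endpoint. The grouped cardiac rate is the figure a reader will look at first. Several Broad terms have ordinary non-cardiac causes in these subjects:

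- Ascites, hepatomegaly and mental status changes can come from liver disease, and Cohorts 6 to 12 are all cirrhotic.
- Nocturia, renal failure and respiratory failure are not specific to the heart.
- To a lesser degree, dyspnoea is among the common simeprevir events in Protocol 1.4.1 ("rash (including photosensitivity), pruritus, nausea, myalgia, and dyspnea"), oedema has hepatic causes, and raised CK is followed in Protocol 7.5.1 as a marker of muscle injury.

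Time to first event is the most exposed output. Protocol 1.4.1 puts 61% of simeprevir dyspnoea events in the first 4 weeks, while Protocol 1.3.2 describes a PR prolongation on odalasvir that had become second-degree AV block by Week 12. In a subject with both, the dyspnoea would set the event time and the conduction event would add nothing to the curve.

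There is also a gap. Only the infarction part of ischaemic heart disease is used, so angina pectoris and myocardial ischaemia are not on the list, while nocturia is.

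**Working it through.** **Term count.** Transcribing SAP 11.4.3 gives 202 Narrow and 264 Broad rows, 466 in all. Many terms repeat across SMQs, leaving 379 distinct terms. Of these, 181 are Narrow in at least one SMQ, so 379 − 181 = 198 are Broad only (198/379 = 52%).

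| Terms | Status in 11.4.3 |
|---|---|
| Ascites, hepatomegaly, dyspnoea, nocturia, CK increased | Broad only |
| Bradycardia, heart rate decreased, syncope, left ventricular dilatation, ventricular hypertrophy | Broad only |
| PR prolongation, first- and second-degree AV block, QRS and QT prolongation, ejection fraction decreased | Narrow |

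The second row shows why a narrow-only rule would be wrong here. Slowed heart rate, left ventricular dilatation and hypertrophy are among the animal findings in Protocol 1.3.1, and a narrow-only group would drop the matching terms.

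**Chance of a background case.** The plan gives no figure for this grouping. The formula behind its detection probabilities in Protocol 9.3 is 1 − (1 − p)^n. With n = 320 it returns 95.99%, 27.4%, 79.9% and 92.35% for p = 1%, 0.1%, 0.5% and 0.8%, against the stated 96%, 27%, 80% and 92%.

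The same formula applies with b, the share of subjects who have a listed term for a non-cardiac reason. The value of b is an assumption, because the documents do not give it.

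| Assumed b | Cohort of 10 | Cohort of 20 |
|---|---|---|
| 2% | 18% | 1 − 0.98^20 = 33% |
| 5% | 40% | 1 − 0.95^20 = 64% |
| 10% | 65% | 1 − 0.90^20 = 88% |

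One such subject moves a cohort of 20 by 1/20 = 5 percentage points.

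**Share of flagged subjects with a specific cardiac event.** Let s be the specific cardiac rate, also assumed, and independent of b. The composite rate is 1 − (1 − s)(1 − b), and the share is s divided by that. For example, s = 1% and b = 5% give a composite of 1 − 0.99 × 0.95 = 5.95% and a share of 1/5.95 = 17%.

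| | b = 2% | b = 5% | b = 10% |
|---|---|---|---|
| s = 1% | 34% | 17% | 9% |
| s = 5% | 72% | 51% | 34% |

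**Ischaemia gap.** The infarction terms in 11.4.3 include unstable and postinfarction angina, and chest pain appears as Broad under cardiomyopathy. Angina pectoris and myocardial ischaemia appear nowhere. Protocol Appendix F grades new ischaemic symptoms, with stable angina as its example, as Grade 3 cardiac ischemia. An event the trial grades as severe could therefore miss the cardiac group.

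**The case against.** The strongest reply is that a sensitive grouping suits an exploratory safety trial and partly matches the protocol's own surveillance. Protocol 7.5.2 treats dyspnea, orthopnea and pedal edema as possible signs of heart failure that call for echocardiography. Protocol 7.5.1 pairs CK with CK-MB or troponin, and Protocol 7.2.2 lets a laboratory change count as an AE only under stated conditions. This stands: dyspnoea, oedema and CK increased belong in the broad version.

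A reader might infer that the drug's real cardiac signal is obscured. The documents do not support that. SAP 8.3.2 reports centrally read PR, QRS and QTc categories and lists subjects with progressive PR prolongation. SAP 8.3.3 tabulates ejection fraction decline and left ventricular volumes and wall thickness. SAP 8.1 tabulates TEAEs by preferred term, and listing 16.2.7.5 shows each event of special interest. These outputs do not replace the grouped ones, however, because the ECG and echocardiogram tables carry neither AE relationship nor time to first event.

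A reader might also infer that non-cardiac cases will outnumber true events several-fold. The tempting arithmetic has two parts:

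- Decompensation at 5% per year (Protocol 1.1) over 32 to 36 weeks is 0.05 × 32/52 = 3.1% to 0.05 × 36/52 = 3.5%. In the 70 to 140 subjects of Cohorts 6 to 12, that is about 2 to 5.
- A 3% dyspnoea excess in 60 + 19 + 70 to 140 = 149 to 219 simeprevir-treated subjects is about 4 to 7.

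These would be set against the one conduction case reported among 123 dosed subjects. The comparison fails. The 5% is for cirrhosis in general, whereas this trial takes Child-Pugh A subjects and excludes those with low albumin, raised bilirubin or a history of decompensation. The dyspnoea excess was seen with peginterferon and ribavirin. The one case is a noted clinical finding, not a count of cardiac AEs, and Protocol 1.3.2 reports PR above 200 msec in 4 of 32 volunteers on odalasvir. In this trial's own data (Protocol 1.2.1.2), no term on the cardiac list is among those with 6 or more events. That caps any single listed term at 5 events in 123 subjects (4.1%), but it does not bound their sum.

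**Conclusion.** The concern holds as a point about scope and interpretability. The cardiac group has no stated narrow or broad rule, most of its distinct terms are Broad only, and terms with common non-cardiac causes enter every grouped cardiac output. The grouped incidence and time to first event are diluted; the underlying signal stays visible elsewhere.

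The size of the dilution cannot be derived from the documents. The 33% to 88% range for cohorts of 20 rests on an assumed background of 2% to 10%, and the shares also rest on an assumed specific rate and independence. That every Broad term counts is inferred from the unrestricted list. If the sponsor intended otherwise, the SAP should say so, which is much the same edit. Whether the list is complete against MedDRA 19.1 cannot be checked here. The ischaemia gap rests on no assumption about rates.

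**What to change.** Before database lock, amend SAP 8.1 and Appendix 4 as follows:

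- Keep the present grouping, labelled as the broad (sensitive) version, with dyspnoea, oedema and CK increased in it.
- Add a second version of the cardiac table, the Kaplan-Meier analysis and the worst-grade chart, shown by SMQ. It would use all Narrow terms plus pre-named Broad terms that match the odalasvir findings: bradycardia, heart rate decreased, syncope, palpitations, left ventricular dilatation, left ventricular dysfunction and ventricular hypertrophy. Cardiac arrest belongs here too and is already Narrow under the shock SMQ.
- Add angina pectoris and myocardial ischaemia to the list.
- Correct the pointer in 11.4.1, which sends the reader to Appendix 3 for the cardiac terms.

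The cost is a term-list edit and one extra row or figure per output, with no new data, since every term already carries its Narrow or Broad label. The narrower version is less sensitive, which the broad version beside it covers.
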